Official title: Estimating the Sensitivity of a Mobile Neuro-cognitive Platform ("BrainE") to Detect Neural Plasticity and Cognitive Enhancements Following Theta-burst Stimulation to Superior Frontal/dACC TMS Stimulation.

NCT number: NCT03946059

Document Date: February 16th 2021

**Study Protocol:** Participants provided written informed consent for the TMS study protocol approved by the UCSD IRB (#190059). Participants were screened for this study prior to enrollment. Any individuals with a history of seizure disorder; vascular, traumatic, tumoral, infectious or metabolic lesion of the brain; administration of drugs that lower the seizure threshold; implanted or non-removable metallic objects above the neck; implanted devices with electrical circuits (pace-makers, cochlear implants) were excluded from enrollment. In addition, subjects were excluded if they had chronic sleep deprivation or confirmed heavy alcohol use (defined as greater than 5 episodes of binge drinking in the past month with >5 alcohol drink-equivalents per sitting for men (or >4 drink-equivalents per sitting for women). Subjects were also excluded if they reported the use of stimulant drugs in the past month (cocaine, methamphetamines), or if they were pregnant, or had any history of severe cardiovascular disease (i.e. history of transient ischemic attack, heart attack or stroke).

Repetitive Transcranial Magnetic Stimulation (rTMS). We used the FDA-approved Magventure stimulator (MagPro R30) for rTMS delivery. Each participant made two visits for this study, separated by a one-week interval, and each visit lasted up to 2 hours. Participants were provided either the continuous theta burst stimulation (cTBS) or intermittent TBS (iTBS) TMS protocol at each visit. Participants were blinded to the stimulation type, and stimulation order in week 1 or 2 was counterbalanced across subjects. The research staff who performed stimulation were blind to the effects of the cTBS or iTBS protocol, and the data analytics lead and study principal investigator were blind to the identity of the protocol i.e. all data were analyzed with cTBS blinded as stim A and iTBS as stim B. TBS stimulation was delivered to the midline at FCz target location, consistent with the pre-supplementary motor area site for rTMS in superior frontal cortex, which was active in most of our cognitive tasks (Verbruggen et al., 2010). A train of 3 pulses, spaced 20 msec apart (50 Hz stimulation), followed by an inter-train interval of at least 200 msec (5 Hz) was applied either continuously (cTBS), or intermittently (iTBS) with a jitter between trains as has been tested in prior research (Rossi, Hallett, Rossini, Pascual-Leone, et al., 2009; Oberman et al., 2011). In cTBS, bursts of 3 pulses at 50 Hz were applied at a frequency of 5 Hz for 20 sec, total 100 bursts. In iTBS, ten 2 sec periods (10 bursts) of TBS were applied at a rate of 0.1 Hz for a total 100 bursts. Stimulation amplitude was set at 80% of motor threshold individually determined in each participant.

At each rTMS study visit, participants first performed a set of neuro-cognitive assessments (pre-stim), then immediately received either cTBS or iTBS TMS stimulation, then performed the neuro-cognitive assessments again (post-stim). We investigated the sensitivity of the neuro-cognitive assessments to measure brain plasticity in pre-stim versus post-stim comparisons, as a function of the rTMS protocols. Details of the neuro-cognitive assessments are provided in Balasubramani, et al., Mapping Cognitive Brain Functions at Scale. Neuroimage 2021 *in Press* https://doi.org/10.1016/j.neuroimage.2020.117641

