## Statistical Analysis Plan:

For neural analyses for the primary outcome, we applied a uniform processing pipeline to all EEG data acquired simultaneous to the cognitive tasks. This included: 1) data pre-processing, and 2) cortical source localization of the EEG data filtered within the relevant theta frequency bands.

For the secondary outcome, behavioral data for cognitive assessments were analyzed for signal detection sensitivity, d', computed as z(Hits)-z(False Alarms) (Heeger and Landy, 2009). Task speeds were calculated as log(1/RT); RT is response time acquired in milliseconds then converted to RT in seconds to be used in the log speed calculation. Then, task efficiency was calculated as a product of d' and speed (Barlow et al., 1980; Vandierendonck, 2017), and global task efficiency was the average efficiency across all cognitive tasks.

Both for the primary (neural) and secondary (behavioral) outcome, data were compared across stimulation type (iTBS vs cTBS) using repeated measures analyses of variance (rm-ANOVA) with a within-subject factor of task-type; the Tukey-Kramer method was used for post-hoc testing.

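### The two-visit crossover is analysed by an rm-ANOVA that names no visit term, so any visit difference in pre-to-post gain stays in the error of the iTBS–cTBS contrast

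*Combined protocol and SAP*

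**What the plan says.** The section on Repetitive Transcranial Magnetic Stimulation (rTMS) sets out the design. "Each participant made two visits for this study, separated by a one-week interval". One protocol, cTBS or iTBS, was given at each visit, and "stimulation order in week 1 or 2 was counterbalanced across subjects". At each visit the assessments were done before and after stimulation, so every participant met them four times. The stated interest is in "pre-stim versus post-stim comparisons, as a function of the rTMS protocols".

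The analysis is one sentence, in the last paragraph of the Statistical Analysis Plan, covering both the neural (primary) and behavioural (secondary) outcomes. Stimulation types are compared by rm-ANOVA "with a within-subject factor of task-type", with Tukey-Kramer post-hoc tests. No visit, week, period, order or sequence term is named anywhere. The number of participants, in total or per order, is not given.

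**The concern.** The design controls order, but the stated analysis makes no use of that. In a two-period crossover, counterbalancing and a period term do different jobs. Counterbalancing makes the visit effect cancel from the mean iTBS–cTBS difference. It does not stop the visit effect from pushing individual differences up in one order and down in the other. Unless visit is in the model, that spread is counted as error.

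Comparing pre with post removes practice that is common to both visits. What is left is any change in the gain itself from week 1 to week 2, for example a smaller gain once the tasks are familiar. The plan does not say whether gains or post-stimulation values enter the rm-ANOVA. If post-stimulation values are compared directly, all visit-to-visit practice remains as well.

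Precision is what is at stake. An overstated standard error makes a real difference between the protocols easier to miss, in a study whose title gives its aim as estimating how sensitively the platform detects plasticity.

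**Working it through.** **Inputs.** From the documents: two visits per participant, one protocol per visit, order counterbalanced, and no visit term named. There is no stated sample size, SD, alpha or power, so there is no figure of the plan's own to reproduce. Assumed: N = 12, 20 or 40; two-sided 5% test; one paired difference per participant; equal orders unless stated.

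**Model.** Let d be a participant's iTBS-minus-cTBS difference in gain:

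d = τ + s·p + e, with SD(e) = 1

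Here s = −1 if iTBS came first and +1 if cTBS came first. p is the visit 2 minus visit 1 shift in gain, in units of the residual SD of d after visit is removed.

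**Effect on the error.** With equal orders the mean of d has expectation τ and true variance 1/N, whatever p is.

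- With a visit term, the error variance is 1 on N−2 degrees of freedom.
- Without it, the expected error variance is 1 + p²·N/(N−1), about 1 + p², on N−1 degrees of freedom.

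So the estimated standard error is multiplied by about √(1 + 0.25²) = √1.0625 = 1.03 at p = 0.25, and by √(1 + 0.5²) = √1.25 = 1.12 at p = 0.5.

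**Power.** τ is set to give exactly 80% power with the visit term. Without the term, the sum of squares is noncentral chi-square with N−1 degrees of freedom and noncentrality N·p².

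| N | τ | Power without term, p = 0 | p = 0.25 | p = 0.5 | Break-even p |
|---|---|---|---|---|---|
| 12 | 0.898 | 80.8% | 78.8% | 72.8% | 0.16 |
| 20 | 0.662 | 80.2% | 78.4% | 72.6% | 0.09 |
| 40 | 0.455 | 80.1% | 78.2% | 72.7% | 0.04 |

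Above the break-even p, the visit term gains more than its degree of freedom costs. If there is no visit shift, it costs 0.8, 0.2 or 0.1 percentage points of power. At p = 1, power without the term falls to about 50%.

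**Test size, N = 20, equal orders, no visit term.** The nominal 5% becomes 4.4% at p = 0.25 and 2.9% at p = 0.5, so the test is conservative.

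**Unequal orders (hypothetical).** If a share f received iTBS first, the bias has size p·|2f − 1|. For a 12:8 split, f = 0.6, so it is 0.2·p: 0.05 at p = 0.25 and 0.10 at p = 0.5. In simulations of 200,000 runs at N = 20, test size without the visit term was:

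| Split | p = 0.25 | p = 0.5 |
|---|---|---|
| 12:8 | 4.9% | 4.5% |
| 14:6 | 6.4% | 9.8% |

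A 12:8 split therefore does not inflate the error rate; 14:6 does. With the visit term, test size stayed between 4.9% and 5.1% throughout.

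**If stimulation type is not modelled as paired.** The variance factor is then 1 + p²(1 − ρ)/2, with ρ the between-visit correlation. At an assumed ρ = 0.5 this is 1 + p²/4. The standard error is multiplied by √1.0156 = 1.008 at p = 0.25 and √1.0625 = 1.03 at p = 0.5.

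**The case against.** The strongest reply is that this is conditional and may be small. With equal orders there is no bias and no excess of false positives, so a positive finding is not undermined. Nothing in the documents shows that gain differs between visits. At p = 0.25 the loss is only one to two points of power, and the larger loss needs a shift of half a residual SD after common practice has cancelled. All of this stands and limits the point to precision.

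A second reply is that the SAP lists task-type as its only within-subject factor, so stimulation type may not have been paired at all. In that case the visit term matters less than the pairing: at ρ = 0.5, failing to pair multiplies the standard error by 1/√(1 − 0.5) = 1.41, against at most 1.03 from the visit shift for p up to 0.5. This also stands. The power figures above hold for a paired analysis only. Whether stimulation was paired is a separate question, though, and does not remove the case for a visit term.

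Third, one sentence may not list every term. It also omits any pre/post factor, although the rTMS section says that comparison was of interest. A visit term may have been fitted and not reported. If so, saying so settles the matter.

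**Conclusion.** The point holds. The plan describes a counterbalanced two-visit crossover and names no visit term in its only model statement. If that sentence lists the whole model, any visit difference in gain inflates the estimated error of the iTBS–cTBS contrast.

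The size cannot be found from the documents. For a paired analysis with equal orders, a visit shift of 0.25 to 0.5 residual SD would cost roughly 1 to 7 points from 80% power; with no shift, nothing is lost. Bias would arise only if the analysed orders were unequal. The documents do not suggest that they were, but without the numbers per order a reader cannot check.

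The change should be made because it is standard and cheap. It does not put a positive result in doubt. Confidence is medium, because the model description is so brief.

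**What to change.** - State whether stimulation type was a within-participant factor, how pre and post entered the model, and whether visit was fitted.
- If visit was not fitted, add it (week 1 vs week 2) as a within-participant fixed effect in the primary and secondary models, and report the iTBS–cTBS contrast adjusted for it.
- Report the number of participants analysed in each order.
- An order main effect is optional; it does not change the within-participant contrast.

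The document is written in the past tense, so this would be a re-analysis or sensitivity analysis, labelled as added after the original analysis. The cost is one re-run of each model and, in the paired comparison, one error degree of freedom. The visit is known for every session, so no new data are needed.

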## Statistical Analysis Plan:

For neural analyses for the primary outcome, we applied a uniform processing pipeline to all EEG data acquired simultaneous to the cognitive tasks. This included: 1) data pre-processing, and 2) cortical source localization of the EEG data filtered within the relevant theta frequency bands.

For the secondary outcome, behavioral data for cognitive assessments were analyzed for signal detection sensitivity, d', computed as z(Hits)-z(False Alarms) (Heeger and Landy, 2009). Task speeds were calculated as log(1/RT); RT is response time acquired in milliseconds then converted to RT in seconds to be used in the log speed calculation. Then, task efficiency was calculated as a product of d' and speed (Barlow et al., 1980; Vandierendonck, 2017), and global task efficiency was the average efficiency across all cognitive tasks.

Both for the primary (neural) and secondary (behavioral) outcome, data were compared across stimulation type (iTBS vs cTBS) using repeated measures analyses of variance (rm-ANOVA) with a within-subject factor of task-type; the Tukey-Kramer method was used for post-hoc testing.

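### Does the lack of a stated rule for hit or false-alarm rates of 0% or 100% undermine the d' outcome?

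*Combined protocol and SAP*

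**What the plan says.** The Statistical Analysis Plan builds the secondary outcome in three steps. It defines d' as "signal detection sensitivity, d', computed as z(Hits)-z(False Alarms", with a literature citation attached. Next, "task efficiency was calculated as a product of d' and speed", where speed is the log of inverse response time. Finally, "global task efficiency was the average efficiency across all cognitive tasks". Both outcomes then go into the same model: "data were compared across stimulation type (iTBS vs cTBS) using repeated measures analyses of variance (rm-ANOVA", with task type as a within-subject factor.

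The protocol's section on repetitive TMS has each participant attend twice and complete the tasks before and after stimulation each time, so each task is scored 2 × 2 = 4 times per person. For trial counts and other task specifics it points elsewhere: "Details of the neuro-cognitive assessments are provided in" a published paper. On blinding it says that "all data were analyzed with cTBS blinded as stim A and iTBS as stim B".

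Neither part of the document mentions a correction, a clip, an exclusion or a missing-value rule for rates of 0% or 100%.

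**The concern.** The z-transform of 0 is minus infinity and that of 1 is plus infinity. A participant who hits every target, or never makes a false alarm, therefore has no finite d' under the formula as printed. With both rates at 100%, or both at 0%, the difference is undefined. Because efficiency multiplies d' and global efficiency averages over tasks, one such task makes the global score for that run non-finite too.

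Someone would then have to choose how to proceed, and the choice can matter. Dropping the affected runs selects on the outcome. Clipping at an arbitrary value lets that value set the largest scores in the data. If boundary runs were common, the behavioural result could rest partly on a decision the reader cannot see.

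**Working it through.** The documents give no d' value, sample size, trial count, accuracy level or number of tasks, so there is no figure of theirs to reproduce. Trial counts and rates below are assumptions, with n targets and n non-targets per task-run (one task in one pre- or post-stimulation run).

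**1. How often is the boundary reached?** With true hit rate H and false-alarm rate F,

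P(boundary) = 1 − (1 − Hⁿ − (1−H)ⁿ)(1 − Fⁿ − (1−F)ⁿ).

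| n of each kind | H / F | P(boundary) |
|---|---|---|
| 100 | 80% / 10% | 0.003% |
| 60 | 90% / 5% | 4.8% |
| 30 | 90% / 5% | 24.8% |
| 20 | 95% / 2% | 78.7% |

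The range runs from practically never to most of the time. Carrying a rate over to participants widens it further. If 5% of task-runs were affected, the share of participants with at least one would be 5% if all fell in the same people. With independence it would be 1 − 0.95¹² = 46% for 12 task-runs each, or 1 − 0.95²⁴ = 71% for 24.

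**2. How much does the choice of rule matter?** Two standard corrections are the log-linear rule, (x + 0.5)/(n + 1) for every rate, and the 1/(2n) rule, which replaces 0 by 1/(2n) and 1 by 1 − 1/(2n).

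| Run | n | Log-linear | 1/(2n) |
|---|---|---|---|
| All hits, no false alarms | 20 | 3.96 | 3.92 |
| | 30 | 4.28 | 4.26 |
| | 60 | 4.80 | 4.79 |
| All hits, 10% false alarms | 20 | 3.16 | 3.24 |
| | 30 | 3.35 | 3.41 |
| | 60 | 3.65 | 3.68 |

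For 24 of 30 hits and no false alarms, log-linear gives z(24.5/31) − z(0.5/31) = 2.95 and 1/(2n) gives z(0.8) − z(1/60) = 2.97. The largest gap among these boundary runs is 3.24 − 3.16 = 0.08.

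On the efficiency scale, at an assumed response time of 0.5 s and natural logs, the two rules give 2.746 and 2.717 for a perfect run at n = 20, a gap of 0.029. Averaging over several tasks makes it smaller still in the global score.

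A large spread appears only with fixed clips. A perfect run scores 4.65, 6.18 or 9.51 with rates clipped at 0.01, 0.001 or 0.000001. None of these clips appears in the documents.

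**3. What would imposing a rule do?** Log-linear scoring of every run also moves values that are already finite. At 90% hits and 10% false alarms, d' falls from 2.56 to 2.36 (n = 20), 2.42 (n = 30) or 2.49 (n = 60). At 29/30 hits and 1/30 false alarms it falls from 3.67 to 3.32. If one rule was already applied throughout, rescoring would alter sound values for no gain.

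**The case for a change.** The best case for a change is that standard practice here is not a single practice. Log-linear, 1/(2n), fixed clips and exclusion are all possible, and they do not all agree. Even the mild 0.01 clip gives 4.65 for a perfect run at n = 20, against about 3.9 under the two standard rules. With 30 targets, going from 28 to 29 hits moves d' by 0.33. Going from 29 to 30 moves it by 0.48 under log-linear, but by 2.92 under a clip at 0.000001. The cited assessment paper is offered for task details, whereas scoring is laid out in the analysis plan itself. Stating the rule would take one sentence.

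Part of this stands. The rule is not written down here, and an extreme clip or the removal of boundary runs would be poor choices. But nothing indicates that either was made. The analysis plan attaches a signal-detection reference to the d' formula, and a correction could be in that source or in the assessment paper; neither can be checked. The result depends on an unstated choice only if at least one boundary run occurred, and that is not known. Analysis under coded stimulation labels limits any choice that favours one protocol. The comparison is within-subject with counterbalanced order, and boundary runs include liberal and conservative responding as well as perfect performance, so no direction of bias can be named.

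**Conclusion.** No change to the plan follows. The formula is not finite at 0% or 100% and no rule is stated, but this is a detail that competent analysts fill sensibly, and one they are forced to notice: an infinite score makes the means and sums of squares in the ANOVA non-finite. With either standard correction, the choice moves a boundary run's d' by at most 0.08 in the cases worked above, and by at most 0.04 for a perfect run. Only the secondary behavioural measures are involved.

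This rests on two assumptions: that equal trial counts of 20 to 60 of each kind are representative, and that one rule was used for all tasks, visits, runs and stimulation types. The frequency of boundary runs remains unknown. The conclusion would change if study records showed that boundary runs were dropped, clipped at an extreme value, or handled differently between runs or protocols. Naming the correction used and counting the affected runs is good practice when the results are reported, but the plan does not need to be altered for it.

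### Does leaving the Tukey-Kramer family and the sphericity handling unstated undermine the iTBS-versus-cTBS analysis?

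*Combined protocol and SAP*

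**What the plan says.** The final paragraph of the Statistical Analysis Plan covers both outcomes in one sentence. It opens "Both for the primary (neural) and secondary (behavioral) outcome" and continues that "data were compared across stimulation type (iTBS vs cTBS) using repeated measures analyses of variance (rm-ANOVA) with a within-subject factor of task-type". After a semicolon it adds that "the Tukey-Kramer method was used for post-hoc testing". No other error control is named, and no sphericity check, correction or alternative covariance model is mentioned.

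For the behavioral outcome the same section also defines a single summary: "global task efficiency was the average efficiency across all cognitive tasks". The protocol's account of the study visits gives the aim as measuring "brain plasticity in pre-stim versus post-stim comparisons, as a function of the rTMS protocols".

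The documents do not state the number of tasks, the sample size or the significance level.

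**The concern.** Tukey-Kramer controls error over all pairs within a stated set of means, and here the set is not stated. Three are possible: the task types, the two stimulation types within each task, or every stimulation-by-task cell. If the aim is to say in which tasks iTBS and cTBS differ, the question is one contrast per task, and none of the three fits it well. Pairs of task types answer a different question. Two levels within a task amount to an unadjusted t-test, so nothing is controlled across tasks. All cells spend most of the protection on pairs nobody asked about.

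The classical F-tests for task-type and for stimulation by task also assume sphericity. For the interaction, this fails when the iTBS-minus-cTBS differences have unequal variances across tasks.

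What would be at stake is how a reader interprets a statement that a particular task responded differently: it could have been tested very strictly or with no correction across tasks.

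**Working it through.** There is no stated figure to reproduce. Everything below is illustration.

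**Inputs.** Stimulation has two levels (SAP, final paragraph). The number of tasks *k* is not given; the rTMS paragraph says of the target site "which was active in most of our cognitive tasks", which suggests at least three. Assumed: *k* = 3 to 6, *n* = 20, two-sided alpha 0.05, equal variances unless noted.

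**Step 1: the main comparison.** With two levels, Tukey's critical value is the ordinary *t*: q(0.95; 2, 19)/√2 = 2.093 = t(0.975; 19). A single contrast on one degree of freedom has no sphericity condition. The same holds for global task efficiency, which is already averaged over tasks. In simulation with unequal task variances, the main effect's type I error was 4.7% to 5.2% in every setting.

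**Step 2: the three possible families.**

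| Family | Pairs, *k* = 3 → 6 | Critical *t*, *k* = 3 → 6 |
|---|---|---|
| Pairs of task types | k(k−1)/2 = 3 → 15 | 2.54 → 3.16 (19 df) |
| All stimulation-by-task cells | k(2k−1) = 15 → 66 | 2.91 → 3.31 (pooled error); 3.16 → 3.70 (paired error, 19 df) |
| Two stimulation types within each task | 1 per task | 2.09 |
| For reference: Bonferroni over *k* paired contrasts | 3 → 6 | 2.63 → 2.94 |

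- *Pairs of task types.* This is the textbook use, and error over those pairs is controlled, subject to sphericity. With five tasks all responding equally (standardized difference 0.8, correlation 0.3), Tukey on the iTBS-minus-cTBS differences flagged some pair of tasks in 5.8% of runs. That is close to nominal for the question it asks, whether tasks differ.
- *All cells.* Conservative for per-task contrasts: their family-wise error is 1.4% (*k* = 3) to 0.6% (*k* = 6). A contrast with 80% power under Bonferroni has 72% to 70% with pooled error, or 64% to 57% with paired error. With pooled error the loss is only 1 to 2 points at *n* = 12 and 10 to 14 points at *n* = 30.
- *Within each task.* Liberal if run without a preliminary F-test: 1 − 0.95³ = 14% and 1 − 0.95⁶ = 26% for independent tasks, or 12% to 19% at correlation 0.6. If a significant interaction is required first and nothing differs, at most about 5%. If one task truly differs (standardized difference 0.8 to 1.2), the remaining tasks are effectively uncorrected. The ceilings for independent tasks are 1 − 0.95² = 9.75% and 1 − 0.95⁵ = 22.6%; simulation gives about 7.5% to 9% (*k* = 3) and 17% to 22% (*k* = 6), against 4% to 5% with Holm.

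**Step 3: sphericity.** Type I error of the uncorrected stimulation-by-task F-test, when one task's difference has a larger SD than the rest:

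| SD ratio | Uncorrected |
|---|---|
| 1.5 | 5.4% to 6.0% |
| 2 | 6.0% to 8.0% |
| 3 | 7.1% to 7.6% (*k* = 3); 9.6% to 11.3% (*k* = 6) |

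Greenhouse-Geisser gives 3.8% to 5.1% throughout these settings. It has its own cost: when sphericity holds, it runs at 2.6% to 2.7% with *k* = 6 and *n* = 12.

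**Step 4: the proposed replacement.** Holm-adjusted paired contrasts control error across tasks, but with *k* = 6, correlation 0.6 and effect 0.8, power is 73%, against 91% for unadjusted per-task tests that follow a significant interaction.

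**The case for a change.** The best case for amending the plan starts from its logic. Stimulation has only two levels, so post-hoc testing has a purpose only if tasks come into it. The aim is how sensitively the assessments pick up stimulation effects, which makes a per-task statement a natural next step. The same sentence governs the primary outcome. Two of the possible families err in opposite directions, so a reader who meets a per-task claim cannot tell how strictly it was tested. A few sentences would settle the matter.

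Much of this stands. The sentence is incomplete, and the incompleteness is not an artifact of redaction or text extraction. The arithmetic also holds on the stated assumptions.

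It does not show that the planned analysis is wrong. The comparison the plan announces is between stimulation types, and no passage promises a verdict on individual tasks. Task-type is the one named factor likely to have three or more levels, so all pairs of its levels is the most literal reading, and there the method fits. Silence about a sphericity correction is not evidence that none was used, and nothing in the documents supports a three-fold SD ratio.

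**Conclusion.** The concern does not call for a change. What is missing is a description of follow-up testing that an analyst would ordinarily supply: the family, any preliminary F-test and the sphericity handling. Naming these when results are reported is normal practice. The main iTBS-versus-cTBS effect and the global efficiency comparison are untouched on any reading.

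The possible harm needs a per-task claim that the plan does not make. Its direction is not fixed either: 0.6% to 1.4% family-wise error if all cells were compared, 12% to 26% if each task was tested alone with no preliminary F-test. The sphericity effect is about one percentage point at most for a 1.5-fold SD ratio, and reaches 9.6% to 11.3% only with six tasks and a three-fold ratio.

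Replacing Tukey-Kramer with Holm would be a trade-off, with an illustrated power cost of 91 − 73 = 18 points. Because the plan is written in the past tense, it would also mean choosing a new method after the data had been analyzed. Every error and power figure here rests on assumed values for the number of tasks, sample size, alpha, correlation, SD ratio and effect size, none of which the documents give.
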